9.9. Planned subgroup analyses

Interpretation of subgroup analysis will be treated with caution with output treated as hypothesis generating rather than definitive⁹.

Analysis will be limited to the primary outcome and the following subgroups:

- Gender (Male, Female)
- Modified EHRA (Class 1/2a, Class 2b/3/4)
- Receiving beta-blocker therapy within 1 month of randomisation (No, Yes)
- Age (<75 years, ≥75 years)
- Left Ventricular Ejection Fraction (<50%, ≥50%)

The effects of these subgroups will be examined by including a treatment group by subgroups interaction parameter in the linear regression model.

A template for reporting is given in Appendix D9.

9.10. Sensitivity analyses

Sensitivity analyses will be limited to the primary outcome only and will consist of:

- Per-protocol analysis (population described in sections 5.3 and 5.4)
- Adjust the final model for additional covariate of baseline apical heart rate
- SF36v2 questionnaire completed outside the pre-specified visit window of ± 4 week's

We have stated in the protocol that we will allow a ± 4 week's window for the follow up visits and so any questionnaires for SF36v2 at 6 months completed outside this time window will be excluded in this sensitivity analysis.

- Analysis to assess the impact of missing data (see below for method)

Missing data will be imputed using multiple imputation with chained equations in Stata 16 (or above). Stata's "MI" command will be used to carry out this analysis and the "regress" option will be used since the primary outcome is continuous data. 50 imputations will be generated for any missing data for primary outcome (i.e. SF36v2 PCS score at 6 months) and all minimisation variables (Gender, EHRA score), treatment arm, baseline PCS score and any other baseline data deemed appropriate will be used to aid the multiple imputation procedure. Imputed results will be combined using Stata's "mi estimate" command.

10. Analysis of sub-randomisations

N/A

11. Health economic analysis

Health economic analysis is planned for this trial and will be described separately in the health economic analysis plan by the health economist for the trial.

12. Statistical software

Statistical analysis will be undertaken in the following statistical software packages:

- Stata version 15 (or higher)
- SAS software, version 9.4 (or higher)

13. References

[figure not shown]

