4.6. Randomisation

Participants will be randomised in a 1:1 ratio to either Digoxin 62.5 – 250 µg od or Bisoprolol 1.25 – 15 mg od. The time between randomisation and commencement of trial therapy should be minimised (ideally <24 hours).

Randomisation will be provided by a computer generated programme at the Birmingham Clinical Trials Unit (BCTU), using a minimisation algorithm incorporating the following factors:

- Baseline EHRA (class 1/2a and class 2b/3/4)
- Gender (Male and Female)

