4.7. Sample size

Randomising 144 patients we can assume an 85% power to detect an effect size of half a standard deviation in a continuous outcome measure of QoL (two-sided alpha of 0.05).

A sample size of 160 patients would account for an estimated 10% loss to follow-up (including withdrawal and death prior to 12-month assessment).

There is some evidence from existing research to support the notion that the treatment effect could be this large. The mean SF-36 role-physical score from the rate-control arm of the RACE study was 47, with a 17% improvement with rate-control over time.² In another study, CCB resulted in 22% improvement in a proprietary symptom-checklist, compared to a non-significant 8% change in those assigned to beta-blockers (SD 10-points in both groups). These values are also consistent with a 17% improvement in SF-36 scores in a third trial, PIAF.³

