9.3. Handling missing data

In the first instance, analysis will be completed on received data only with every effort made to follow-up participants even after protocol violation to minimise any potential for bias. To examine the possible impact of missing data on the results, and to make sure we are complying with the intention-to-treat principle, sensitivity analysis will be performed on the primary outcome measure only.⁸ See section 9.10 for further details.

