9.6. Analysis methods – secondary outcomes

A template for reporting all the secondary outcomes is given in Appendix D6.

Patient-reported QoL

For the RATE-AF trial, questionnaires SF-36v2, EQ-5D-5L and AFEQT are administered at baseline, 6 months and 12 months.

Up-titration visits:

These questionnaires are also administered for each patient at their last up-titration visit.

Note: the data for last up-titration visit is not done at any scheduled time-point due to the fact that each patient will have different up-titration visits (i.e. some will have 6 and some may only have 1) and so for this reason the data collected for last up-titration visit will only be summarised by treatment arm and no formal analysis for this data will be conducted.

- **SF-36v2 global and domain specific scores at 6 and 12 months**

The data for these outcomes are continuous in nature and the computation for the global and domain specific scores is described in the data manipulations section 9.4. The mean and standard deviation along with minimum and maximum values for global and domain specific scores will be presented by treatment arm and time-point.

The global and domain-specific scores will be analysed separately at 6 and 12 months using the same analysis methods as described in section 9.5. for primary outcome:

- Physical component summary (PCS) score at 12 months
- Mental component summary (MCS) score at 6 months and 12 months
- Physical Function score at 6 months and 12 months

- Role Limitation Due to Physical Problems score at 6 months and 12 months
- Role Limitation Due to Emotional Problems score at 6 months and 12 months
- Social Functioning score at 6 months and 12 months
- Mental Health score at 6 months and 12 months
- Energy/Vitality score at 6 months and 12 months
- Pain score at 6 months and 12 months
- General Health Perception score at 6 months and 12 months

The range for each domain of the SF-36v2 is from 0=worst score to 100=best score. The Bisoprolol arm will again be used as a reference category for all model based analysis for SF-36v2 and so higher values will indicate better outcome for Digoxin arm.

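### The planned missing-data analysis imputes 6-month PCS from baseline variables only, so it will nearly repeat the complete-case result and does not test informative dropout

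*SAP*

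**What the plan says.** The primary analysis uses received data only (SAP 9.3; Protocol 12.3.3). SAP 9.5 regresses the 6-month PCS on arm, baseline PCS, the minimisation variables, age and baseline LVEF.

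SAP 9.3 gives the check on this to a sensitivity analysis: "To examine the possible impact of missing data on the results", and to honour intention-to-treat. SAP 9.10 describes that analysis as multiple imputation by chained equations: "50 imputations will be generated for any missing data for primary outcome". The named predictors are gender, EHRA, arm and baseline PCS, after which "any other baseline data deemed appropriate will be used to aid the multiple imputation procedure". No post-baseline predictor is named. There is no missing-not-at-random analysis and no rule for PCS after death.

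Three other places bear on this:

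- **Other PCS visits.** The SF-36 is also completed at 12 months, and SAP 9.6 adds: "These questionnaires are also administered for each patient at their last up-titration visit". The same section limits the up-titration scores to summaries by arm, because that visit falls at no fixed time.
- **Repeated-measures model.** SAP 9.6 plans a mixed model for PCS with unstructured covariance as an additional secondary analysis. It assumes a constant treatment effect first. Estimates by visit follow only if the treatment-by-time interaction has p<0.05.
- **Deaths.** SAP 9.4 scores the EQ-5D index as 0 for participants who die before completing it. PCS has no such rule.

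**The concern.** A sensitivity analysis for missing data is informative when it changes the assumption about the missing values, or brings in information that the primary analysis did not use. This one does little of either. It keeps the missing-at-random assumption and conditions on almost the same baseline variables. Agreement between the two results could then be read as evidence that missing data do not matter, although the method would show that agreement in most settings.

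Informative loss is plausible here. The trial is open-label with a patient-reported primary outcome, and Protocol 8.7 foresees withdrawals related to adverse symptoms. If patients doing badly on one drug are more often the ones without a 6-month questionnaire, both analyses would carry nearly the same bias.

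The open wording on what is imputed also means that, as written, a participant who died before 6 months would be given the PCS of a living patient.

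**Working it through.** **1. The plan's own figures.** SAP 4.7 gives "Randomising 144 patients we can assume an 85% power to detect an effect size of half a standard deviation" with "two-sided alpha of 0.05", and SAP 4.6 states "Participants will be randomised in a 1:1 ratio".

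- n per arm = 2(z₀.₉₇₅ + z₀.₈₅)²/d² = 2(1.960 + 1.036)²/0.5² = 71.8, so 72 per arm and 144 in total.
- Power at 72 per arm is 0.851 (normal) or 0.846 (noncentral t).
- "A sample size of 160 patients would account for an estimated 10% loss to follow-up": 144/0.90 = 160.

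The sample size reproduces and is not in question. Two figures guide the amount of missing data: the 10% loss in SAP 4.7, and the 85% completion target in Protocol 3.4, which implies up to about 15% missing.

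**2. Why the two estimates nearly coincide.** Let X be the covariates and b the complete-case coefficients. If only the outcome is missing and the imputation uses the same X, the imputed values average X_mis·b over many draws. The completed-data normal equations are then

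X′X·β = X_obs′y_obs + X_mis′X_mis·b = X_obs′X_obs·b + X_mis′X_mis·b = X′X·b,

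so β = b. Imputation adds only Monte Carlo noise. A gap can open only through auxiliaries outside the analysis model.

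**3. Simulation.** Settings: 160 patients, true effect 0, the SAP covariate set, 50 imputations and 600 trials per row. The documents do not give the following inputs, so they are assumptions: correlation of 6-month PCS with baseline PCS 0.6 and with the post-baseline PCS 0.8; coefficient of one extra baseline predictor 0.2; and the missingness rates and mechanisms. The post-baseline PCS was taken as available for everyone, which is a best case. Entries are mean bias in SD units. With a standard error near 0.13 SD, the Monte Carlo error is about 0.13/√600 = 0.005.

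| Driver of missingness | Missing, by arm | Complete case | MI, same covariates | MI + extra baseline variable | MI + post-baseline PCS |
|---|---|---|---|---|---|
| Baseline PCS | 5% v 15% | 0.001 | 0.001 | 0.001 | 0.001 |
| Extra baseline variable | 5% v 15% | 0.023 | 0.024 | −0.002 | 0.008 |
| Post-baseline PCS | 5% v 15% | 0.064 | 0.063 | 0.061 | 0.001 |
| Post-baseline PCS | 10% v 20% | 0.070 | 0.069 | 0.065 | 0.006 |
| Unseen 6-month PCS | 5% v 15% | 0.083 | 0.083 | 0.079 | 0.042 |
| Unseen 6-month PCS | 10% v 20% | 0.072 | 0.071 | 0.068 | 0.030 |
| Post-baseline PCS | 10% v 10% | −0.002 | −0.002 | −0.002 | −0.003 |

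With the same covariates, the mean absolute gap between imputation and complete case was 0.004–0.006 SD, with correlation about 0.999. One extra baseline variable widened the gap to 0.010–0.013 SD, or to 0.025 SD when that variable itself drove the unequal loss.

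**4. A harsher assumed pattern.** Here loss was 10% at random in one arm and 17% driven by poor 6-month PCS in the other, with visit correlations of 0.55–0.75 in the first run. Two separate simulations of this pattern gave:

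- 0.114 SD for both complete case and baseline-only imputation, falling to 0.086 with the up-titration PCS and 0.064 with the 12-month PCS also added;
- 0.103 SD (complete case) and 0.104 SD (baseline-only), falling to 0.060 with the 12-month PCS and 0.047 with both.

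In each, the mean gap between baseline-only imputation and complete case was 0.009 SD.

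**5. Size against the design effect.** 0.064/0.5 = 13% and 0.114/0.5 = 23%.

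**6. What a delta analysis would show.** Lowering the imputed values in one arm by δ shifts the difference by (fraction missing) × δ:

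- 10% × 0.5 SD = 0.05 SD (10% of 0.5 SD)
- 15% × 0.5 SD = 0.075 SD (15%)
- 15% × 1 SD = 0.15 SD (30%)

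**The case against.** The strongest reply is that the SAP already has an analysis that uses other PCS visits. A participant with a 12-month but no 6-month score contributes to the mixed model in SAP 9.6. In a simulation with 10% random v about 16% informative loss, baseline PCS adjusted for (SAP 9.6 does not list it as a covariate) and the 12-month PCS always available, bias was 0.086 SD for complete case, 0.049 SD for the mixed model at 6 months and 0.022 SD for its constant effect. With the 12-month score available for only half of those missing at 6 months, the figures were 0.096, 0.077 and 0.054 SD. This stands: the plan does contain an estimate that could differ visibly from the primary one. But that model is not designated for missing data, it assumes a constant effect first, and it is still missing-at-random.

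A reader might infer that imputation must equal complete case. The documents do not support that, because SAP 9.10 allows extra baseline variables. The second row of the table shows that the right one can remove a bias.

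Other points also stand in part:

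- The up-titration scores were set aside for a stated reason, irregular timing. That is a reason against a formal comparison at that visit, and less so against using the score as an auxiliary.
- Questionnaires are mailed to those who stop treatment but accept follow-up (Protocol 8.7), and missing questionnaire data are monitored (Protocol 9.5.2). This lowers the loss but does not reach those who refuse follow-up.
- Appendix D7 of the SAP already tabulates deaths by arm with reasons, though not those before 6 months.

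**Conclusion.** The concern holds in a limited form. The analysis that SAP 9.3 relies on will give nearly the complete-case answer, exactly so up to Monte Carlo noise if no further auxiliary is added, and it does not test informative dropout. No other planned analysis relaxes missing-at-random.

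Under assumed unequal informative loss, the bias that would pass unseen is roughly 0.06–0.11 SD. If the trial SD were 10 points, which the documents do not state, that is about 0.6–1.1 PCS points. If loss is similar in size and mechanism in both arms, the bias is about zero. The correlations, loss rates and mechanisms are all assumptions.

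A reader might go further and infer that the primary result will be biased or the trial underpowered. Neither follows: the documents do not show that loss will be unequal or informative, and the sample size reproduces. The effect of imputing PCS after death has not been quantified; that part rests on the wording of SAP 9.10 and its contrast with the EQ-5D rule.

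**What to change.** Amend SAP 9.10 as follows.

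- **(a) Imputation model.** Add the 12-month PCS, and the last up-titration PCS where available. Make a matching edit to the sentence in SAP 9.6 that limits up-titration data to summaries, so that use as an imputation auxiliary is allowed. Name the baseline auxiliaries too. The gain depends on how many participants missing at 6 months have another post-baseline score.
- **(b) Missing-not-at-random analysis.** Add a delta-adjusted (tipping-point) version, shifting the imputed values separately by arm over a range stated in advance, and report the shift at which the conclusion changes. The documents give no basis for a particular range, so the trial team should choose and justify one. This part is needed even with (a): when the unseen 6-month PCS drove the loss, 0.030–0.064 SD of bias remained after post-baseline scores were added.
- **(c) Deaths.** Do not impute PCS after death. Report deaths before 6 months by arm.

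The cost is a little more analysis and a few table rows. No new data are needed, and the primary analysis and sample size do not change.

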Appendix A: Deviations from SAP

This report below follows the statistical analysis plan dated <insert effective date of latest SAP> apart from following:

Section of report not following SAP	Reason

Appendix B: Trial schema

Inclusion Criteria:

- Age 60 years or older
- Permanent AF, characterised as a physician decision for rate control only
- Breathless; New York Heart Association Class II or above
- Able to provide written informed consent

[figure not shown]
Exclusion criteria:

- Established indication for beta-blocker therapy (e.g. myocardial infarction in the last 6 months)
- Known contraindication for beta-blockers or digoxin (e.g. history of severe bronchospasm or known intolerance)
- Baseline heart rate <60 bpm, 2nd/3rd degree block, accessory pathway or history of ventricular arrhythmia
- Planned pacemaker implantation, pacemaker-dependent rhythm or previous atrioventricular node ablation
- Decompensated heart failure within 14 days requiring intravenous inotropes, vasodilators or diuretics
- Hypertrophic cardiomyopathy, myo/pericarditis or previous/planned heart transplant
- Receiving renal replacement therapy
- Major surgery within 3 months or severe concomitant disease expected to reduce life expectancy

Appendix C: Schedule of assessments

Procedures		Baseline Visit	Up-titration Visits (Day 14 to 60)	Visit 2, Month 6 (± 4 weeks)	Visit 3, Month 12 (± 4 weeks)
Assessment of eligibility criteria		X			
Informed consent taken		X			
Review of medical history		X			
Review of medications		X	X	X	X
Physical exam	Complete	X			
	Symptom-directed		X	X	X
	Vital signs	X	X	X	X
Quality of life assessment		X	(X)	X	X
Functional and cognitive assessment		X		X	X
Transthoracic echocardiogram		X			X
12-lead electrocardiogram		X		X	X
6-minute walk test		X		X	X
24-hour ambulatory ECG			X	(X)	
Clinical labs	Chemistry	X		X	X
	Haematology	X		X	X
	Serum digoxin			(X)	(X)
Trial labs	BNP	X		X	
	Stored sample	X		X	
Assessment of compliance			X	X	X
Assessment of adverse events			X	X	X

Appendix D1: CONSORT flow diagram

Appendix D2: Baseline characteristics

Baseline data	Digoxin (N=)	Bisoprolol	Total (N=)
Age (Years)			
Mean [SD]			
Med {IQR}			
Min - Max			
Gender*			
Female			
Male			
Creatinine (micromol/L)			
Mean [SD]			
Med {IQR}			
Min - Max			
On anticoagulant before randomisation			
No			
Yes			
EHRA class*			
1			
2a			
2b			
3			
4			
NYHA class			
I ^f			
II			
III			
IV			
Previous diagnosis of heart failure?			
No			
Yes			
Any signs of heart failure at baseline			
No			
Yes			
Type I diabetes			
No			
Yes			
missing			
Type II diabetes			
No			
Yes			
missing			
Unplanned admission for AF or HF in last 12 months			
No			
Yes			
Any previous cardioversions			
No			

	Yes Number of cardioversions (Min – Max)			
Previously undergone AF ablation	No Yes Number of ablations (Min – Max)			
Previous history of anti-arrhythmic drugs	No Yes			
Baseline NTproBNP (pg/mL)	N Mean [SD] Med {IQR} Min - Max			
Radial artery heart rate (bpm)	Mean [SD] Med {IQR} Min - Max			
Apex beat heart rate (bpm)	Mean [SD] Med {IQR} Min - Max			
12-Lead ECG Heart Rate (bpm)	N Mean [SD] Med {IQR} Min - Max			
Systolic BP (mmHg)	N Mean [SD] Med {IQR} Min - Max			
Self-declared ethnicity	White - English / Welsh / Scottish / Northern Irish / British White - Irish Asian / Asian British – Indian Asian / Asian British – Pakistani Black / African / Caribbean / Black British – Caribbean Black / African / Caribbean / Black British – African			
Estimated ejection fraction	Mean [SD] Median {IQR} Min-Max <40% 40-49% ≥50%			

**Minimisation variables
(Note: categories of the EHRA class for the minimisation algorithm were combined into EHRA class 1/2a and EHRA class 2b/3/4)*

Appendix D3: Adherence to allocated intervention

Adherence to treatment allocation based on actual medication taken

Adherent to treatment allocation		Digoxin	Bisoprolol	Total
At 6 months	N			
	No			
	Yes			
	If yes, taking additional rate control therapy			
At 12 months	N			
	No			
	Yes			
	If yes, taking additional rate control therapy			

Oral medication type by treatment arm and time point

Medication*	6 months			12 months		
	Digoxin	Bisoprolol	Total	Digoxin	Bisoprolol	Total
Digoxin						
B-blocker						
Diltiazem						
Verapamil						
Amiodarone						
Other						

*Medications not mutually exclusive

Adherence assessed by asking the patient

Medication taken	6 months			12 Months		
	Digoxin (N=)	Bisoprolol (N=)	Total (N=)	Digoxin (N=)	Bisoprolol (N=)	Total (N=)
All						
Some						
>75%						
>50-75%						
>25-50%						
≤25%						
None						
Missing						

Appendix D4: Protocol deviations and violations

List of patients with follow-up visits conducted outside the specified ± 4 week's window by treatment arm

Digoxin (N=xx)

1)

2)

...

Bisoprolol (N=xx)

1)

2)

...

Appendix D5: Primary outcome results

SF-36v2 physical component summary (PCS) score at 6 months

Primary outcome	Time point	Statistic	Digoxin	Bisoprolol	Linear regression model	
					Adjusted mean difference ¹ 95% CI	P-value ¹
Intention to treat analysis						
PCS	Baseline	N Mean [SD] Min - Max			-	-
	6 months	N Mean [SD] Min - Max				
Sensitivity Analysis – Multiple imputation for missing data						
PCS	Baseline	N Mean [SE]			-	-
	6 months	N Mean [SE]				
Per-Protocol analysis (i.e. adherent to treatment allocation and remained in permanent AF at 6 months)						
Included in per-protocol analysis set	6 months	No			-	-
		Yes				
		Total				
PCS	Baseline	N Mean [SD] Min - Max			-	-
	6 months	N Mean [SD] Min - Max				

¹-Adjusted for treatment arm, baseline score, all minimisation variables, age at randomisation and baseline LVEF

Reference group for the treatment arm in the model is Bisoprolol arm

Higher values indicate better scores so a positive mean difference favours Digoxin arm

Appendix D6: Secondary outcomes results

SF-36v2 global and domain specific scores at 6 and 12 months

Secondary outcome	Time point	Statistic	Digoxin	Bisoprolol	Linear regression model	
					Adjusted mean difference ¹ 95% CI	P-value ¹
Physical Component Summary (PCS)						
PCS	Baseline	N Mean [SD] Min - Max			-	-
	12 months	N Mean [SD] Min - Max				
Mental Component Summary (MCS)						
MCS	Baseline	N Mean [SD] Min - Max			-	-
	6 months	N Mean [SD] Min - Max				
	12 months	N Mean [SD] Min - Max				
Physical Function Domain score (PF)						
PF	Baseline	N Mean [SD] Min - Max			-	-
	6 months	N Mean [SD] Min - Max				
	12 months	N Mean [SD] Min - Max				
Role Limitation Due to Physical Problems Domain score (RP)						
RP	Baseline	N Mean [SD] Min - Max			-	-
	6 months	N Mean [SD] Min - Max				
	12 months	N Mean [SD] Min - Max				
Role Limitation Due to Emotional Problems Domain score (RE)						
RE	Baseline	N Mean [SD] Min - Max			-	-
	6 months	N Mean [SD] Min - Max				
	12 months	N Mean [SD] Min - Max				

Social Functioning Domain score (SF)						
SF	Baseline	N Mean [SD] Min - Max			-	-
	6 months	N Mean [SD] Min - Max				
	12 months	N Mean [SD] Min - Max				
Mental Health Domain score (MH)						
MH	Baseline	N Mean [SD] Min - Max			-	-
	6 months	N Mean [SD] Min - Max				
	12 months	N Mean [SD] Min - Max				
Energy/Vitality Domain score (EV)						
EV	Baseline	N Mean [SD] Min - Max			-	-
	6 months	N Mean [SD] Min - Max				
	12 months	N Mean [SD] Min - Max				
Pain score (Pain)						
Pain	Baseline	N Mean [SD] Min - Max			-	-
	6 months	N Mean [SD] Min - Max				
	12 months	N Mean [SD] Min - Max				
General Health Perception Domain score (GHP)						
GHP	Baseline	N Mean [SD] Min - Max			-	-
	6 months	N Mean [SD] Min - Max				
	12 months	N Mean [SD] Min - Max				

1-Adjusted for treatment arm, baseline score, all minimisation variables, age at randomisation and baseline LVEF

Reference group for the treatment arm in the model is Bisoprolol arm

Higher values indicate better scores so a positive mean difference favours Digoxin arm

EQ-5D-5L summary index and visual analogue scale at 6 and 12 months

Secondary outcome	Time point	Statistic	Digoxin	Bisoprolol	Linear regression model	
					Adjusted mean difference ¹ 95% CI	P-value ¹
EQ-5D-5L summary index score[£]						
EQ-5D-5L summary index score	Baseline	N Mean [SD] Min - Max			-	-
	6 months	N Mean [SD] Min - Max				
	12 months	N Mean [SD] Min - Max				
EQ-5D-5L visual analogue scale (VAS) score[§]						
EQ-5D-5L VAS score	Baseline	N Mean [SD] Min - Max			-	-
	6 months	N Mean [SD] Min - Max				
	12 months	N Mean [SD] Min - Max				

1-Adjusted for treatment arm, baseline score, all minimisation variables, age at randomisation and baseline LVEF

£-The range for summary index is from -0.285=worst score to 1=best score

§-The range for visual analogue score is from 0=worst score to 100=best score

The Bisoprolol arm will be used as a reference category and so positive mean difference will indicate better outcome for Digoxin arm

AFEQT overall score at 6 and 12 months

Secondary outcome	Time point	Statistic	Digoxin	Bisoprolol	Linear regression model	
					Adjusted mean difference ¹ 95% CI	P-value ¹
AFEQT overall score[£]						
AFEQT overall score	Baseline	N Mean [SD] Min - Max			-	-
	6 months	N Mean [SD] Min - Max				
	12 months	N Mean [SD] Min - Max				

1-Adjusted for treatment arm, baseline score, all minimisation variables, age at randomisation and baseline LVEF

£-The range for visual analogue score is from 0=worst score to 100=best score

The Bisoprolol arm will be used as a reference category and so positive mean difference will indicate better outcome for Digoxin arm

Echocardiographic LVEF at 12 months

Echocardiographic LVEF	Time point	Statistic	Digoxin	Bisoprolol	Linear regression model	
					Adjusted mean difference ¹ 95% CI	P-value ¹
LVEF	Baseline	<40%			-	-
		40-49%				
	≥50%					
	N					
		Mean [SD]				
		Min - Max				
LVEF	12 months	<40%			-	-
		40-49%				
	≥50%					
	N					
		Mean [SD]				
		Min - Max				

1-Adjusted for treatment arm, baseline score, all minimisation variables, age at randomisation, baseline LVEF, history of myocardial infarction (MI) at baseline, coronary angioplasty or stents (PCI) at baseline and coronary artery bypass surgery (CABG) at baseline

Reference group for the treatment arm in the model is Bisoprolol arm

Higher values indicate better scores so a positive mean difference favours Digoxin arm

Diastolic function (E/e' and composite of diastolic indices) at 12 months

Diastolic function	Time point	Statistic	Digoxin	Bisoprolol	Linear regression model	
					Adjusted mean difference ¹ 95% CI	P-value ¹
E/e'	Baseline	N			-	-
		Mean [SD]				
	Min - Max					
	N					
		Mean [SD]				
		Min - Max				
E/e'	12 months	N				
		Mean [SD]				
	Min - Max					
	N					
		Mean [SD]				
		Min - Max				

1-Adjusted for treatment arm, baseline score, all minimisation variables, age at randomisation and baseline LVEF

Reference group for the treatment arm in the model is Bisoprolol arm

Higher values indicate better scores so a positive mean difference favours Digoxin arm

Diastolic function	Time point	Statistic	Digoxin	Bisoprolol	Logistic regression model	
					Adjusted Odds Ratio ¹ 95% CI	P-value ¹
Composite of diastolic indices	Baseline	No			-	-
		Yes				
	No					
	Yes					
		No				
		Yes				
Composite of diastolic indices	12 months	No				
		Yes				
	No					
	Yes					
		No				
		Yes				

1-Adjusted for treatment arm, baseline score, all minimisation variables, age at randomisation and baseline LVEF

Reference group for the treatment arm in the model is Bisoprolol arm

Higher values indicate better scores so an odds ratio >1 favours Digoxin arm

Change in heart rate

Secondary outcome	Time point	Statistic	Digoxin	Bisoprolol	Linear regression model	
					Adjusted mean difference ¹ 95% CI	P-value ¹
Radial Heart (bpm)						
Radial Heart rate (bpm)	Baseline	N Mean [SD] Min - Max			-	-
	6 months	N Mean [SD] Min - Max				
	12 months	N Mean [SD] Min - Max				
Apical Heart rate (bpm)						
Apical Heart rate (bpm)	Baseline	N Mean [SD] Min - Max			-	-
	6 months	N Mean [SD] Min - Max				
	12 months	N Mean [SD] Min - Max				
12-lead ECG Heart rate (bpm)						
12-lead ECG Heart rate (bpm)	Baseline	N Mean [SD] Min - Max			-	-
	6 months	N Mean [SD] Min - Max				
	12 months	N Mean [SD] Min - Max				
24-hour ambulatory average Heart rate (bpm)						
24-hour ambulatory Heart rate	24-hour	N Mean [SD] Min - Max				

¹-Adjusted for treatment arm, baseline score, all minimisation variables, age at randomisation and baseline LVEF

The Bisoprolol arm will be used as a reference category

Six-minute walking distance at 6 and 12 months

Six-minute walking test	Digoxin (N=)	Bisoprolol (N=)	Total (N=)
6 months follow-up			
Did the patient undergo the 6-min walk test? No Yes Missing			
If yes: Total time spent (min/s) Median {IQR} Min - Max Total distance covered (m) Median {IQR} Min - Max Was the test stopped prematurely? No Yes			
12 months follow-up			
Did the patient undergo the 6-min walk test? No Yes Missing			
If yes: Total time spent (min/s) Mean [SD] Median {IQR} Min - Max Total distance covered (m) Mean [SD] Median {IQR} Min - Max Was the test stopped prematurely? No Yes			

Distance covered (in metres) from the 6-minute walk test

Secondary outcome	Time point	Statistic	Digoxin	Bisoprolol	Linear regression model	
					Adjusted mean difference ¹ 95% CI	P-value ¹
Distance (metres)	Baseline	N Mean [SD] Min - Max			-	-
	6 months	N Mean [SD] Min - Max				
	12 months	N Mean [SD] Min - Max				

1-Adjusted for treatment arm, baseline score, all minimisation variables, age at randomisation and baseline LVEF

The Bisoprolol arm will be used as a reference category and so positive mean difference will indicate better outcome for Digoxin arm

Change in European Heart Rhythm Association (EHRA) class at 6 and 12 months

	Time point	Statistic	Digoxin	Bisoprolol	Ordinal Logistic regression model	
					Adjusted odds ratio ¹ 95% CI	P-value ¹
EHRA Class	Baseline	Class 1 Class 2a Class 2b Class 3 Class 4			-	-
	6 months	Class 1 Class 2a Class 2b Class 3 Class 4				
	12 months	Class 1 Class 2a Class 2b Class 3 Class 4				

1-Adjusted for treatment arm, all minimisation variables, age at randomisation and baseline LVEF.

Reference group for the treatment arm in the model is Bisoprolol arm.

Lower odds indicate better outcome so values <1 favours Digoxin arm.

2 class improvement in EHRA class at 6 and 12 months compared to baseline

EHRA Class	Time point	Statistic	Digoxin	Bisoprolol	Logistic regression model	
					Adjusted Odds Ratio ¹ 95% CI	P-value ¹
2 class improvement from baseline	6 months	No Yes				
	12 months	No Yes				

1-Adjusted for treatment arm, baseline score, all minimisation variables, age at randomisation and baseline LVEF

Reference group for the treatment arm in the model is Bisoprolol arm

Higher values indicate better scores so an odds ratio >1 favours Digoxin arm

Change in B-type natriuretic peptide (BNP) (NTproBNP) levels at 6 months

Secondary outcome	Time point	Statistic	Digoxin	Bisoprolol	Linear regression model	
					Ratio of geometric means ¹ 95% CI	P-value ¹
Log-transformed NTproBNP (ng/L)	Baseline	N Mean [SD] Min - Max			-	-
	6 months	N Mean [SD] Min - Max				
	12 months	N Mean [SD] Min - Max				

1-Adjusted for treatment arm, baseline score, all minimisation variables, age at randomisation and baseline LVEF

Reference group for the treatment arm in the model is Bisoprolol arm

Lower ratio indicates better scores so values <1 favours Digoxin arm

